### **C. Evaluate Edema**

On page 2 of the Response Sheet, record the presence or absence of tumor-associated the severity of edema, and the location of tumor-associated edema, if present.

In addition, lower extremity edema should be measured. Measure the circumference, in centimeters, of the ankle at the level of the malleoli and of the calf at a point 10 cm below the lower border of the patella. This must be done at entry in all participants whether there is edema or not. For patients with lower extremity edema, consider also documenting edema at the level of the thigh and pelvis. For each measurement, note the distance from an anatomical landmark.

#### **D. Perform Oral Examination**

An oral mucosal tissue examination will be conducted on all study participants to detect the presence of oral cavity KS lesions.

The recommended standardized oral mucosal tissue examination should be conducted wearing gloves and 2x2 inch gauze and light. The oral examination should be conducted in the following sequence:

##### *Lips*

Begin examination by observing the lips, with the mouth both closed and opened. Note the color, texture, and any surface abnormalities of the upper and lower lip.

##### *Labial Mucosa*

With the mouth partially open, visually examine the lower labial mucosa by pulling the lower lip and stretching it over the chin, holding it between your thumb and index finger and using both hands. Repeat the same steps for the examination of the upper labial mucosa by pulling the upper lip and stretching it over the nose.

##### *Buccal Mucosa and Vestibules*

With the mouth open wide, examine first the right buccal mucosa (inside of cheek) extending from the labial commissures (corner of the lips) and back to the anterior tonsilar pillar. Examine both the upper and lower vestibule using the mirror to stretch the buccal mucosa and to help visualize the posterior vestibules. Examine the left buccal mucosa, following the same guidelines.

##### *Hard and Soft Palate*

With the mouth wide open and the participant's head tilted backwards, inspect the hard palate (note the ridges or rugae) located in the anterior part, and then the soft palate and uvula (ask the participant to say "ahhh" to better visualize the soft palate).

##### *Tongue*

With the participant's tongue at rest and mouth partially open, inspect the dorsum of the tongue for any swelling, ulceration, coating or variation in size, color, or texture. Also note any change in the pattern of the papillae covering the surface of the tongue and examine the top and the tip of the tongue. The participant should then protrude the tongue, and the examiner should grasp the tip of the tongue with a piece of gauze to assist with full protrusion and allow examination of the margins or lateral borders. Note the small "lumps" located on each side of the posterior lateral tongue in the base of tongue area; these are the

foliate papillae (considered to be an extension of the lingual tonsils). Then observe the ventral surface.

*Floor of Mouth*

With the tongue still elevated, inspect the floor of the mouth for swellings or other abnormalities.

*Gingiva*

First, examine the buccal and labial aspects of the gingiva and alveolar ridge. Start with the right maxillary posterior gingiva and alveolar ridge and move around the arch to the left posterior gingiva. Continue with the left mandibular posterior gingiva and alveolar ridge and move around the arch to the right posterior gingiva.

Second, examine the palatal and lingual aspects as has been done on the facial side, from right to left on the palatal (maxilla) and left to right on the lingual (mandible). Use the mouth mirror to retract the posterior part of the tongue and focus the light to better visualize the lingual gingiva.

Record the presence or absence of oral cavity KS lesions and their location on Page 1 of the Worksheet. Note whether lesions are raised or flat.

**E. Evaluating Disease that cannot be Measured by Physical Exam** (Evaluable Disease, Visceral KS)

*Screening and Follow up for Visceral Disease*

A chest X-ray (CXR) will be performed at screening. If the CXR findings are abnormal, additional evaluations are required in consultation with a pulmonologist. Bronchoscopy with visualization of lesions consistent with Kaposi sarcoma or lung biopsy are required for documentation of pulmonary KS. Appropriate microbiologic evaluation to exclude infectious etiologies is required. If pulmonary KS is noted, a CT scan should be performed to document disease.

At screening, potential study participants must be asked about the presence of gastrointestinal (GI) symptoms (odynophagia, nausea, vomiting, rectal bleeding, and/or abdominal pain). **If GI symptoms are present or microcytic anemia are noted at baseline, further evaluations should include stool tests for occult blood and infectious etiologies if infection is suspected.** Consultation with a gastroenterologist for upper and/or lower GI endoscopy is recommended in cases of occult blood loss or unexplained gastrointestinal symptoms. Documentation of gastrointestinal KS requires direct visualization of pigmented lesion(s) consistent with KS on endoscopy (with or without biopsy confirmation).

*Other Sites of Disease*

CT scanning is not required at baseline in patients without other indications for a CT scan. If performed, KS involving other visceral organs or lymph nodes may be detected by advanced imaging techniques (e.g., CT or MRI scan, ultrasound) and confirmed by biopsy. If KS is

confirmed by biopsy in visceral organs, this information should be recorded. If there is an unconfirmed abnormality on a scan or ultrasound, and KS cannot be confirmed by biopsy, that information should be recorded and the abnormality followed during study treatment to determine if it changes.

Note presence of visceral lesions on page 1 of the Worksheet.

### ***Evaluable Disease***

**Evaluable disease (also known as non-measurable disease)** is disease that cannot be measured directly by the size of the tumor but can be evaluated by other methods. For purposes of this study, lesions considered truly non-measurable include: ascites, pleural or pericardial effusions, lymphangitic lung disease, abdominal masses/abdominal organomegaly identified by physical examination that is not measurable by reproducible imaging techniques, bone lesions without an identifiable soft tissue component that can be evaluated by cross-sectional imaging techniques, and lesions that can be identified only by endoscopic, bronchoscopic, or laparoscopic techniques. Changes in the size of other types of disease may not be accurately quantifiable, for example discrete lung lesions on chest x-ray.

**Effusions, when noted, should be evaluated to exclude primary effusion lymphoma whenever feasible before starting therapy.**

For purposes of response assessment, the evaluation of non-measurable disease is used primarily to determine whether an individual has shown tumor progression when evaluation of measurable disease (i.e., cutaneous marker lesions, lesion counts, numbers of raised and flat lesions, edema, visceral disease that is measurable in two dimensions on CT scan) indicates response or stable disease. We will use the standard of “unequivocal progression”, i.e., an overall level of substantial worsening of disease that is of a magnitude that, even in the presence of stable disease or partial response in measurable disease, the treating physician would feel it important to change therapy. This requires clinical judgment on the part of the investigator. For further guidance on the evaluation of non-measurable disease, please refer to the following:

The KS follow-up examination will be performed according to the schedule of events. Tumor evaluation should follow the guidelines noted in Section 1.1 above, and include:

- Record measurements of the longest linear dimension in millimeters and the longest dimension perpendicular to it of the same marker lesion(s) selected at entry;
- Record the total number of raised and flat lesions (in the same areas that were evaluated at entry, either total body or the representative area(s) selected at entry);
- Record the location, size, or characteristics of oral cavity lesions, after the oral mucosal tissue examination is conducted in the same sequence as the oral examination at entry;

- Record the severity of edema and the location of tumor-associated edema. If no edema was present at entry and no edema is present on the follow-up visit, repeat measurements are not required. If there was no edema at entry and edema develops at a follow-up visit, a re-measure at each KS follow-up evaluation is required. If edema was noted at entry, a re-measure at each KS follow-up evaluation is required.
- Record changes of visceral KS at the intervals required by the protocol if visceral disease was present at entry, or if symptoms suggesting visceral disease develop.

## 2. Calculating Response Status

Response status will be classified as complete response (**CR**), partial response (**PR**), stable disease, or progressive disease (**PD**). For a detailed definition of the KS response status, please refer Section 12.3 of the protocol, as well as reference article provided.

Response should be calculated from Baseline. For patients with decreasing tumor area or lesion counts, new thresholds should also be calculated for values at best response and used as a reference for comparison to subsequent values. **Document Response for Baseline and Response from additional time points (by Date or cycle number) on Page 2 of the Response Sheet.**

### 2.1 Calculate Response Status Based on Area of Marker Lesion(s)

To calculate the KS response status **based on area of marker lesions** you will need the area of the indicator lesions from entry. Next, calculate the area of the same indicator lesion(s) for the current visit. Subtract the area at the current visit from the area at entry, then divide this difference by the area at entry. **Multiplying by 100%** will give you the percentage change from entry. After a participant has had a **confirmed CR or PR**, subsequent measurements for PD should also be compared with the “best response” seen at a previous visit.

**An initial confirmed PR** is a  $\geq 50\%$  decrease in the area of the indicator lesion(s) compared to entry lasting for at least 4 weeks. For example, if a participant had an area of the indicator lesions of  $4000\text{mm}^2$  at entry and an area of the indicator lesions of  $2000\text{mm}^2$  at week 3, and this decrease was maintained for at least 4 weeks, the participant would have a **confirmed PR**.

PD is considered a  $\geq 25\%$  increase in the area of the indicator lesion(s) compared to entry or best response. For example, if the same participant as in the example above had an area of the indicator lesions of  $5000\text{mm}^2$  at week 3, the participant would have PD. Similarly, if a participant had an area of the indicator lesions of  $4000\text{mm}^2$  at entry and an area of the indicator lesions of  $2000\text{mm}^2$  at week 9 **that lasted for four weeks** (a **confirmed PR**) but at a subsequent visit was found to have an area of  $3000\text{mm}^2$  (a greater than 25% increase over the best response), the participant would have PD. **PD after a confirmed CR is defined by the presence of any KS following that confirmed CR.**

***Note: If a confirmed CR has been achieved and subsequent evaluations do not meet criteria for CR, this would be reported as PD.***

Please note that "best response" may improve after the initial **confirmed PR** is documented. For example, if the **entry** area of the indicator lesions was  $5000\text{mm}^2$  and the area decreased to  $2400\text{mm}^2$  at weeks **9 and 15**, this would be the initial **confirmed PR**. If, at week 18, the area of the indicator lesions decreased further to  $2000\text{mm}^2$ , then  $2000\text{mm}^2$  is the new "best response". In this example, subsequent assessments of PD for the area of indicator lesions would be with respect to the number  $2000\text{mm}^2$ , not to  $2400\text{mm}^2$ . Thus, if the area of the indicator lesions at week 24 increased from  $2000$  to  $2500\text{mm}^2$ , this increase would constitute PD, despite the fact that  $2500\text{mm}^2$  is 50% smaller than the entry lesion area.

**Note:** If a confirmed PR has been achieved and subsequent evaluations do not meet criteria for PD or CR, this would continue to be reported as PR. In the example above, if the entry area of the indicator lesions was  $5000\text{mm}^2$  and the area decreased to  $2400\text{mm}^2$  at weeks 9 and 15, and remained at  $2400\text{mm}^2$  at week 18,  $2400\text{mm}^2$  is the "best response" to date. If, at week 24, the area of the indicator lesions increased to  $2800\text{mm}^2$  this would continue to be reported as a PR because  $2800$  is less than a 25% increase from  $2400$ . Similarly, if at week 24, the area of the indicator lesions decreased by an additional 10% to  $2160\text{mm}^2$ , this would also continue to be reported as a PR.

## 2.2 Calculate Response Status Based on the Number of Lesions

To calculate the response status based on the total number of lesions, you will need the total number of lesions (either whole body or, in the case of participants with over 50 lesions at entry, in the combined representative areas) from the entry KS exam. After an initial **confirmed CR** or **PR**, the percentage change for PD should be calculated from the "best response" seen at a previous visit.

**An initial confirmed PR** is a 50% or greater decrease in the number of lesions present at entry (either whole body or, in the case of participants with over 50 lesions at entry, in the combined representative areas) lasting for at least 4 weeks. For example, if a participant had 40 lesions at entry and had only 20 lesions at follow-up and this decrease was maintained for at least 4 weeks, that participant would have a **confirmed PR**.

For participants with  $\leq 50$  cutaneous lesions **at entry**, PD is defined as  $\geq 25\%$  increase in the total lesion count or a minimum of five new lesions, **whichever is greater**, compared to entry or best response. For example, if a participant had 35 lesions at entry and has 44 at follow-up, that would be classified as PD. **PD after a confirmed CR is defined by the presence of any KS following that confirmed CR.**

**Note:** If a confirmed CR has been achieved and subsequent evaluations do not meet criteria for CR, this would be reported as PD.

For participants with  $> 50$  cutaneous lesions **at entry**, PD is defined as  $\geq 25\%$  increase in the total number of lesions **or a minimum of five new lesions, whichever is greater**, in the combined prospectively-defined anatomic sites containing representative lesions **compared**

**to entry or best response**, or a total of five new lesions in anatomic sites which were previously documented as having no evidence of cutaneous disease. For example, if a participant had a total of 40 lesions at entry on the back and the right leg and had a total of 50 lesions at follow-up on the back and the right leg that would be classified as PD. Also, if a participant had no lesions at entry on the right arm and had five lesions on the right arm at follow-up that would be classified as PD. Similarly, if a participant had 40 lesions at entry and 20 lesions at weeks **9 and 15 (a confirmed PR)** but at a subsequent visit was found to have 30 lesions (a greater than 25% increase over the best response), the participant would have PD. **PD after a confirmed CR is defined by the presence of any KS following that confirmed CR.**

Please note that "best response" may improve after the initial **confirmed PR** is documented. For example, if the **entry** number of lesions was 30 and the number of lesions decreased to 15 at weeks **9 and 15**, this would be the **initial confirmed PR**. If, at the week 18 evaluation the number of lesions decreased further, e.g., to 10, then **10 is the new "best response"** and subsequent assessments of PD for lesion counts would be with respect to the number 10, not to 15. **Furthermore, if the number of lesions at week 24 increased from 10 to 15, this increase would constitute PD, despite the fact that 15 is 50% smaller than the entry lesion count.**

**Note: If a confirmed PR has been achieved and subsequent evaluations do not meet criteria for PD or CR, this would continue to be evaluated as PR. In the example above, if the entry lesion count was 30 and the number of lesions decreased to 15 at weeks 9 and 15, then 15 is the "best response" to date. If, at week 24, the number of lesions increased to 18, this would continue to be reported as a PR because 18 is less than a 25% increase from 15. Similarly, if at week 24, the number of lesions decreased by an additional 20% to 12, this would also continue to be reported as a PR.**

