### 6.1.2 Other Procedures: Biopsy (core needle, punch or excisional)

Biopsy/tumor tissue will be obtained by punch biopsy, incisional or excisional biopsy. Core needle biopsy or excisional biopsy may be acceptable for visceral lesions depending on clinical circumstance.

**Note:** Baseline tumor biopsy (fresh) may be obtained up to 28 days prior to treatment initiation.

An archival tumor sample obtained within 1 year of screening is allowed if the pre-treatment biopsy is deemed unsafe or technically not feasible.

Tissue based studies will be performed on mandatory biopsies collected at baseline and at 9 weeks, with an optional biopsy at 13 weeks. Biopsy scheduled for collection at 9 weeks will be obtained prior to dosing on Cycle 2, Week 9, Day 1 or at the End of Treatment visit, whichever occurs first. Effect on tumor microenvironment will be assessed by multi-spectral IHC on serial biopsies.

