**A. Identify and Measure Cutaneous Marker Lesions**

***Select Marker Lesions***

Select bi-dimensionally measurable marker lesions for assessing changes in lesion dimensions. Select the largest lesions with clearly defined margins. When available, a minimum of five bi-dimensionally measurable KS cutaneous marker lesions should be selected. If fewer than five bi-dimensionally measurable marker lesions are available, the total surface area of the marker lesion(s) should be  $\geq 700\text{mm}^2$ . To facilitate repeated lesion measurements, the location of each marker lesion should be described in the Marker Lesion Table, recorded on the standard body diagram (Page 3 of Response Sheet, [Appendix E](#)) in relation to body landmarks and other nearby lesions and photographed as described in Section 3.

***Note:*** Lesions used as marker lesions for measuring response to treatment should NOT be the lesions chosen for biopsies for Tumor Marker Assessments.

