### **B. Evaluate Lesion Number (Total and Nodular/Raised)**

#### ***Select Representative Areas***

For participants with  $\leq 50$  total skin lesions, all lesions should be evaluated for changes in number and characteristics. For participants with  $>50$  total skin lesions, choose three representative areas, if possible, for evaluating change in lesion numbers and characteristics (preferably each selected representative area should have at least 5 lesions, and the total number of lesions counted should be at least 20). **If it is not practical to choose three representative areas, the number of areas selected is left to the investigator's clinical judgment.** On Measurement worksheet, note if greater than 50 lesions.

**Note:** A representative area is a single extremity, the back, chest, or face that has lesions similar in characteristics, i.e., nodularity, size, color, and number, to those found on other parts of the body. A representative area does not need to be the area with the largest number of lesions but should contain lesions that are truly representative of those throughout the remainder of the body. **Confluent lesions should be avoided when possible.**

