### 2.3 Calculate Response Status Based on the Total Number of Raised Lesions

To calculate the response status based on the number of raised lesions, you will need the total number of raised **lesions** (either whole body or, in the case of participants with >50 lesions at entry, in the combined representative areas) from the entry KS exam. If, after an initial **confirmed** response, the disease appears to be getting worse, the percentage change **for PD** should be calculated from the "best response" seen at a previous visit.

**An initial confirmed PR** is a complete flattening of at least 50% of all previously raised lesions (i.e., 50% of all nodular or plaque-like lesion become macules) present at entry (either whole body or, in the case of participants with >50 lesions at entry, in the combined representative areas) lasting for at least 4 weeks. For example, if a participant had 30 raised lesions at entry and had only 15 raised lesions at follow-up and this decrease was maintained for at least 4 weeks that would be classified as a **confirmed PR**.

For participants with  $\leq 50$  cutaneous lesions **at entry**, PD is defined as  $\geq 25\%$  increase in the

number of raised lesions (minimum of 5 new raised lesions if there are very few raised lesions, for example <8), compared to entry or best response. For example, if a participant had 20 raised lesions at entry and had 25 raised lesions at follow-up that would be classified as PD. Also, if a participant had 7 raised lesions at entry and had 12 at follow-up that would be classified as PD. **PD after a confirmed CR is defined by the presence of any KS following that confirmed CR.**

**Note: If a confirmed CR has been achieved and subsequent evaluations do not meet criteria for CR, this would be reported as PD.**

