**Partial Response**

**PR** requires at least one of the highlighted criteria in the table below AND all of the categories shown on the same row, when compared to entry.

**Note:** If any of the criteria for PD have been met, even in the presence of a criterion for **PR**, it is considered PD.

**Note:** **PR** is always a comparison to entry even if there has been a prior **PR**.

Criteria for Classifying PR					
Total body or representative areas					
PR Category	Marker lesion area	Number of lesions	Number of raised lesions	Visceral or Oral KS*	Edema
1	Decrease <math>\geq 50\%</math>	<25% Increase	<25% Increase	<25% Increase of measurable lesions without unequivocal worsening of non-measurable disease	No significant increase or new sites
2	<25% Increase	Decrease <math>\geq 50\%</math>	<25% Increase	<25% Increase of measurable lesions without unequivocal worsening of non-measurable disease	No significant increase or new sites

Criteria for Classifying PR					
Total body or representative areas					
PR Category	Marker lesion area	Number of lesions	Number of raised lesions	Visceral or Oral KS*	Edema
3	<25% Increase	<25% Increase	Decrease $\geq 50\%$	<25% Increase of measurable lesions without unequivocal worsening of non-measurable disease	No significant increase or new sites
4	<25% Increase	<25% Increase	<25% Increase	Decrease $\geq 50\%$ of measurable lesions without unequivocal worsening of non-measurable disease or complete disappearance of non-measurable disease	No significant increase or new sites

\*Please note that there is no need to physically measure the visceral or oral KS.

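### Appendix D keeps biopsied lesions out of the marker set but not out of the lesion counts, so complete removal of a lesion at biopsy can yield a partial response in participants with very few counted or raised lesions

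*Combined protocol and SAP*

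**What the plan says.** **Biopsies.** Section 6.1.2 requires tissue at baseline and at week 9 (or at end of treatment, if sooner), with an optional third biopsy at week 13. On method it says: "Biopsy/tumor tissue will be obtained by punch biopsy, incisional or excisional biopsy". Core needle biopsy is a further possibility for visceral lesions, and archival tissue may replace the baseline biopsy when a fresh one is unsafe or not feasible. Excision is allowed, not required.

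**Marker lesions.** Appendix D, 1.1.A: "Lesions used as marker lesions for measuring response to treatment should NOT be the lesions chosen for biopsies for Tumor Marker Assessments".

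**Lesion counts.** Under Appendix D, 1.1.B, in participants with 50 or fewer lesions "all lesions should be evaluated for changes in number and characteristics". Above 50, representative areas are used, with at least 20 lesions counted in all. Follow-up examinations recount the areas that were counted at entry. Neither instruction mentions biopsied lesions.

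**Partial response.** Section 2.2 of Appendix D sets the 50% rule on the total count: an initial confirmed partial response "is a 50% or greater decrease in the number of lesions present at entry". Section 2.3 words the raised-lesion rule as flattening of at least half the raised lesions, but its worked example is a participant who "had 30 raised lesions at entry and had only 15 raised lesions at follow-up", and the table in 2.4 states the criterion as a fall in the number of raised lesions. One route is enough: partial response "requires at least one of the highlighted criteria in the table below AND all of the categories shown on the same row".

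**Endpoint.** Section 9.4.1 takes the best response within 12 months of the first dose as the objective response rate (ORR) and plans subset analyses where a subset has at least 6 participants.

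**The concern.** The authors saw that sampling a lesion would contaminate the response measurement, and they protected marker area against it. The same protection is missing from the two count criteria. The marker rule in fact steers biopsies onto non-marker lesions, which enter the assessment only through those counts.

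The four-week confirmation does not help, because a completely removed lesion does not come back. Nor is there a floor for small numbers: progression by count in 2.2 needs at least five new lesions when counts are low, while partial response has no equivalent minimum.

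Participants with few lesions are eligible and foreseen. Section 3.1.2 asks only for evaluable disease, Appendix D 1.1.A provides for fewer than five markers, and 2.3 makes special provision for very few raised lesions, giving fewer than eight as its example. At stake is a response credited to the drug that was produced by the biopsy, and its passage into duration of response (DOR).

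**Working it through.** **1. The plan's own figures.** Change is taken relative to the entry count. Section 2.2: 40 to 20 lesions is (40 − 20)/40 = 50.0%, a partial response as stated; 35 to 44 is (44 − 35)/35 = 25.7% increase, progression as stated. Section 2.3: 30 to 15 raised lesions is 50.0%. All reproduce.

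**2. Fall due to biopsy alone.** Let n be the entry count and k the number of counted lesions completely removed after the entry count. I assume at most one per biopsy, each time a different lesion. The fall is k/n, and the threshold is met when k/n ≥ 0.5, that is n ≤ 2k.

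| k | Biopsies involved | Largest n meeting 50% |
|---|---|---|
| 1 | week 9 | 2 |
| 2 | week 9 plus either week 13 or a baseline biopsy taken after the entry count | 4 |
| 3 | all three, with baseline taken after the entry count | 6 |

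The baseline biopsy may be up to 28 days before treatment (6.1.2), while the entry examination may be no earlier than 2 weeks before (Appendix D, 1.1). Their order is therefore not fixed. If the biopsy comes first, or tissue is archival, k is at most 2.

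**3. Allowing for the marker rule.** If m marker lesions are never biopsied, the total count is at least k + m and the fall is at most k/(k + m).

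| Retained markers m | k = 1 | k = 2 | k = 3 |
|---|---|---|---|
| 1 | 1/2 = 50.0% | 2/3 = 66.7% | 3/4 = 75.0% |
| 2 | 1/3 = 33.3% | 2/4 = 50.0% | 3/5 = 60.0% |
| 3 | 1/4 = 25.0% | 2/5 = 40.0% | 3/6 = 50.0% |
| 4 | 1/5 = 20.0% | 2/6 = 33.3% | 3/7 = 42.9% |
| 5 | 1/6 = 16.7% | 2/7 = 28.6% | 3/8 = 37.5% |

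On the total count, four or more retained markers rule out a response by biopsy alone.

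**4. More than 50 lesions.** With at least 20 counted, the largest fall in the total count is 3/20 = 15%.

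**5. Raised lesions.** Read as a simple count, the limits of step 2 apply to raised lesions only, whatever the number of flat ones. As an illustration, with 2 raised and 30 flat lesions and one raised lesion excised, the raised count falls by 1/2 = 50% and the total by only 1/32 = 3.1%.

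**6. Confirmation.** A removal at week 9 is visible at week 13 and again at week 18, 5 weeks later. One at week 13 is visible at weeks 18 and 27, 9 weeks apart. Both satisfy the four-week requirement.

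**7. Larger counts.** With 10 lesions a response needs a fall of 5. If 3 were excised, 5 − 3 = 2 true regressions suffice instead of 5.

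**8. Effect on ORR.** One false response among 20 participants is 1/20 = 5 percentage points. The exact 95% interval moves from 0–16.8% (0/20) to 0.1–24.9% (1/20). In a subset of 6 it is 1/6 = 16.7 points.

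**9. After exclusion.** With biopsied lesions out of both counts, the biopsy-only change is [(n − k) − (n − k)]/(n − k) = 0 for every n > k.

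**The case against.** The other side has real points.

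- **The documents are silent.** Nowhere do they say that an excised lesion stays in the comparison. That is true. But the instruction is to count all lesions and then recount the same areas, without exception, so following the text has that effect.
- **Complete removal is needed.** Punch, incisional and core biopsies may leave the lesion in place, and nothing says each biopsy takes a different lesion. This stands as a condition on the finding.
- **The marker rule already protects most participants.** On the total count this stands: the route needs three or fewer retained markers. Three removals are also a stacked case, requiring the optional week 13 biopsy and a baseline biopsy taken after the entry count.
- **Section 2.3 speaks of flattening.** An excised lesion has not flattened, so on that wording it would not qualify. The example and the table use a plain count. The text supports both readings, and sites could differ.
- **ORR is preliminary.** Section 9.4.1 says so and defers a more precise estimate to an expansion cohort. The recommended phase 2 dose rests on tolerability and T-cell effects, not on ORR. This limits the consequence.

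A reader might infer that the biopsies inflate the response rate across the trial. Steps 3 and 4 do not support that: outside the few-lesion cases excision can at most lower the bar. A reader might also infer that the order of biopsy and lesion measurement must be fixed. It need not be. Ordering at weeks 9 and 13 does not help, since the removal shows at the next visit anyway. At baseline, measurement first would conflict with the 28-day biopsy window, because a biopsy on days −28 to −15 precedes any permitted entry examination.

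**Conclusion.** The gap is real and worth closing, within narrow limits. A lesion completely removed by a research biopsy after the entry count is scored as a lasting decrease. Biopsy alone can produce a partial response only at total or raised counts of 2, 4 or 6 or fewer for one, two or three removals. On the total count it also needs no more retained markers than removals, hence at most three. The raised-lesion route can apply at higher total counts, if 2.3 is read as a count.

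This rests on one whole and different lesion per biopsy, on markers never being biopsied, and on nothing else in the relevant row of the response table worsening. How many participants would qualify cannot be derived from the documents, so the 5 points per false response is a unit of effect, not an estimate of bias. A false response would also enter DOR and, under 2.4, make the lowered count the reference for progression, which could bring progression forward. The primary dose-limiting toxicity endpoint is unaffected.

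**What to change.** In Appendix D, 1.1.B, 2.2 and 2.3, state that any lesion biopsied for research is identified on the body diagram and response sheet and excluded from both the entry count and every follow-up count, total and raised. Compute percentage change on unbiopsied lesions only. When a lesion is first biopsied at week 9 or 13, restate the entry count without it. No rule on the order of biopsy and lesion measurement is needed.

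The cost is one added statement in each of the three sections, one line on the response sheet, and slightly fewer lesions in the denominator. No procedure or visit is added. It should be done before data accrue: the response sheet in Appendix E has no field for biopsied lesions, so the correction may not be recoverable later.
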